6.6.2. Vital Signs

Incidence of orthostatic hypotension using postural changes in blood pressure...will be summarized.

6.6.3. Neurological Results

The Neuropathy Impairment Score (NIS) is the sum of scores over all 37 items from both the Left and Right side. The change from baseline to each post-baseline visit in the NIS (using LOCF for missing data), and to both the Last and Worst (largest) change from Baseline (over all post-Baseline visits) will be summarized, and analyzed using Cochran-Mantel-Haenszel test (stratified by the combinations of two stratification factors, last change from Baseline will not be analyzed). The NIS data, the neurological consultation data and the conclusion from neurological examination data will be reported.

The neurological consultation data will be summarized for all subjects.... The “conclusion from the neurological examination” data will be summarized for each timepoint, and then a summary of the final assessment over all neurological examinations for each subject will be provided.

The change from Baseline in the NIS for Weeks 2, 4, 8, 12, 16, 24, and 40 will be analyzed using a CMH test (stratified by the combined levels of the stratification factors) with change categories. Missing data will be imputed using LOCF only. For this analysis, Baseline data will not be carried forward in the case of a post-Baseline observation not being available for use in LOCF. An additional analysis will use the change from Baseline to the largest (worst) post-Baseline value.

The “conclusion from the neurological examination” data will be summarized for each time point and the last subject assessment. In addition the persistence of any neurological examination finding will be summarized, showing the incidence of subjects with new or worsened neurological examination abnormalities (both clinically significant only and also for any finding) for 2, 3, 4, and ≥ 5 consecutive visits.

6.6.4. Immunogenicity

The following assessments of ADA data will be made:

- A listing of individual serum ADA results sorted by treatment group, subject ID and planned visit. The listing will also include the actual test date/times.
- The proportion of subjects who test positive (i.e. develop anti-tanezumab antibodies) and negative will be summarized by treatment group and planned visit. The summary will also include the proportion of subjects who test positive and negative overall in the study.
- Subjects who develop anti-tanezumab antibodies after treatment will be evaluated for the presence of anti-tanezumab neutralizing antibodies, and individual results will be listed.
- Individual subjects with positive ADA results will be evaluated for potential ADA impact on the individual’s PK, NGF, efficacy and safety profile.

6.6.5. Joint Safety Events

The incidence of subjects with any of the joint safety adjudication outcomes of rapidly progressive osteoarthritis (type 1 and type 2), subchondral insufficiency fracture..., primary osteonecrosis, or pathological fracture, and for occurrence of total joint replacement will be shown by number of subjects treated and subject years of exposure (treatment plus follow up periods), for individual treatment groups.

For the joint safety event analyses, the observation period is defined as the time from first SC dose to study completion or discontinuation for subjects who did not have an event, or time from first SC dose to the earliest event for subjects who did have at least one event.

7. INTERIM ANALYSES

7.1. Introduction

Interim analysis is planned for safety as described in the following sections.

7.2. Interim Analyses and Summaries

Safety data will be subject to regular and ongoing reporting and review throughout the study. The details of these interim analyses will be documented in a separate Statistical Analysis Plan. Review of the safety data will be by the tanezumab external Data Monitoring Committee (E-DMC).

A blinded Adjudication Committee will be convened and asked to review all possible or probable joint-related safety events identified by the Central Reader (rapidly progressive osteoarthritis (type-1 or type-2), subchondral insufficiency fractures, primary osteonecrosis, or pathological fracture), total joint replacement as well as investigator reported adverse events of osteonecrosis, rapidly progressive osteoarthritis, subchondral insufficiency fracture or pathologic fracture. Adverse events related to joint safety that the investigator or sponsor considers medically important may also be reviewed by the Adjudication Committee. A stopping rule relating to a set of adjudicated outcomes has been defined, and is described below.

If the blinded Adjudication Committee identifies adjudicated events of rapidly progressive osteoarthritis type 2, subchondral insufficiency fractures..., primary osteonecrosis, or pathological fracture, occurring at a rate that could trigger the protocol-based stopping criteria, an urgent, ad hoc assessment of the events will be made by the E-DMC.

The protocol (or treatment group) stopping rule will be based on the assessment of the number of subjects with adjudicated events of interest (rapidly progressive osteoarthritis type 2, subchondral insufficiency fractures..., primary osteonecrosis, or pathological fracture) during the course of the study. CCI

CCI [REDACTED] *If the protocol-based stopping rule is triggered, the E-DMC will formulate a recommendation whether it is safe to continue dosing in some or all treatment groups or whether the study should be terminated completely. This decision will be made by Pfizer in consultation with the E-DMC.*

A separate set of dosing suspension rules for specified Serious Adverse Events and events consistent with Hy's Law are described in Section 9.6.1 of the protocol.

Programming and review of unblinded outputs will be performed by individuals independent of the study team.

9. APPENDICES

Appendix 1. SUMMARY OF EFFICACY ANALYSES

Note: BL=Baseline

Endpoint	Analysis Set	Statistical Method	Model/ Covariates	Missing Data	Objective
Change from Baseline to Week 16 in WOMAC Pain subscale	ITT	ANCOVA	BL Score, BL diary average pain, Index Joint (Knee/Hip), Highest KL grade (2, 3 or 4), Treatment Group (Study site as a random effect)	Multiple Imputation	Primary Analysis
Change from Baseline to Week 16 in WOMAC Physical Function subscale	ITT	ANCOVA	BL Score, BL diary average pain, Index Joint (Knee/Hip), Highest KL grade (2, 3 or 4), Treatment Group (Study site as a random effect)	Multiple Imputation	Primary Analysis
Change from Baseline to Week 16 in Patient Global Assessment of Osteoarthritis	ITT	ANCOVA	BL Score, BL diary average pain, Index Joint (Knee/Hip), Highest KL grade (2, 3 or 4), Treatment Group (Study site as a random effect)	Multiple Imputation	Primary Analysis
Change from Baseline to Week 16 in WOMAC Pain subscale	ITT	ANCOVA	BL Score, BL diary average pain, Index Joint (Knee/Hip), Highest KL grade (2, 3 or 4), Study Site, Treatment Group, Study Site x Treatment Group (Study site and interaction as random effects)	Multiple Imputation	Additional (Interaction) Analysis
Change from Baseline to Week 16 in WOMAC Pain subscale	ITT	ANCOVA	BL Score, BL diary average pain, Index Joint (Knee/Hip), Highest KL grade (2, 3 or 4), Country, Treatment Group, Country x Treatment Group.	Multiple Imputation	Additional (Interaction) Analysis
Change from Baseline to Week 16 in WOMAC Physical Function subscale	ITT	ANCOVA	BL Score, BL diary average pain, Index Joint (Knee/Hip), Highest KL grade (2, 3 or 4), Study Site, Treatment Group, Study Site x Treatment Group (Study site and	Multiple Imputation	Additional (Interaction) Analysis

			interaction as random effects)		
Change from Baseline to Week 16 in WOMAC Physical Function subscale	ITT	ANCOVA	BL Score, BL diary average pain, Index Joint (Knee/Hip), Highest KL grade (2, 3 or 4), Country, Treatment Group, Country x Treatment Group.	Multiple Imputation	Additional (Interaction) Analysis
Change from Baseline to Week 16 in Patient Global Assessment of Osteoarthritis	ITT	ANCOVA	BL Score, BL diary average pain, Index Joint (Knee/Hip), Highest KL grade (2, 3 or 4), Study Site, Treatment Group, Study Site x Treatment Group (Study site and interaction as a random effect)	Multiple Imputation	Additional (Interaction) Analysis
Change from Baseline to Week 16 in Patient Global Assessment of Osteoarthritis	ITT	ANCOVA	BL Score, BL diary average pain, Index Joint (Knee/Hip), Highest KL grade (2, 3 or 4), Country, Treatment Group, Country x Treatment Group	Multiple Imputation	Additional (Interaction) Analysis
Change from Baseline to Week 16 in WOMAC Pain subscale	PP	ANCOVA	BL Score, BL diary average pain, Index Joint (Knee/Hip), Highest KL grade (2, 3 or 4), Treatment Group (Study site as a random effect)	Multiple Imputation	Sensitivity Analysis (Per protocol)
Change from Baseline to Week 16 in WOMAC Physical Function subscale	PP	ANCOVA	BL Score, BL diary average pain, Index Joint (Knee/Hip), Highest KL grade (2, 3 or 4), Treatment Group (Study site as a random effect)	Multiple Imputation	Sensitivity Analysis (Per protocol)
Change from Baseline to Week 16 in Patient Global Assessment of Osteoarthritis	PP	ANCOVA	BL Score, BL diary average pain, Index Joint (Knee/Hip), Highest KL grade (2, 3 or 4), Treatment Group (Study site as a random effect)	Multiple Imputation	Sensitivity Analysis (Per protocol)
Change from Baseline to Week 16 in WOMAC Pain subscale	ITT	ANCOVA	BL Score, BL diary average pain, Index Joint (Knee/Hip), Highest KL grade (2, 3 or 4), Treatment Group (Study site as a random effect)	BOCF	Sensitivity Analysis
Change from Baseline to Week 16 in WOMAC Physical Function subscale	ITT	ANCOVA	BL Score, BL diary average pain, Index Joint (Knee/Hip), Highest KL grade (2, 3 or 4), Treatment Group (Study site as a random effect)	BOCF	Sensitivity Analysis
Change from Baseline to Week 16 in	ITT	ANCOVA	BL Score, BL diary average pain,	BOCF	Sensitivity Analysis

Patient Global Assessment of Osteoarthritis			Index Joint (Knee/Hip), Highest KL grade (2, 3 or 4), Treatment Group (Study site as a random effect)		
Change from Baseline to Week 16 in WOMAC Pain subscale	ITT	ANCOVA	BL Score, BL diary average pain, Index Joint (Knee/Hip), Highest KL grade (2, 3 or 4), Treatment Group (Study site as a random effect)	LOCF	Sensitivity Analysis
Change from Baseline to Week 16 in WOMAC Physical Function subscale	ITT	ANCOVA	BL Score, BL diary average pain, Index Joint (Knee/Hip), Highest KL grade (2, 3 or 4), Treatment Group (Study site as a random effect)	LOCF	Sensitivity Analysis
Change from Baseline to Week 16 in Patient Global Assessment of Osteoarthritis	ITT	ANCOVA	BL Score, BL diary average pain, Index Joint (Knee/Hip), Highest KL grade (2, 3 or 4), Treatment Group (Study site as a random effect)	LOCF	Sensitivity Analysis
Change from Baseline to Weeks 2, 4, 8, 12, and 16 in WOMAC Pain subscale	ITT	MMRM	BL Score, BL diary average pain, Index Joint (Knee/Hip), Highest KL grade (2, 3 or 4), Time, Treatment Group, Time x Treatment Group (Study site as a random effect)	Multiple Imputation Data	Sensitivity Analysis for Week 16 (Secondary Endpoint Analysis for other time points)
Change from Baseline to Weeks 2, 4, 8, 12, and 16 in WOMAC Physical Function subscale	ITT	MMRM	BL Score, BL diary average pain, Index Joint (Knee/Hip), Highest KL grade (2, 3 or 4), Time, Treatment Group, Time x Treatment Group (Study site as a random effect)	Multiple Imputation Data	Sensitivity Analysis for Week 16 (Secondary Endpoint Analysis for other time points)
Change from Baseline to Weeks 2, 4, 8, 12, and 16 in Patient Global Assessment of Osteoarthritis	ITT	MMRM	BL Score, BL diary average pain, Index Joint (Knee/Hip), Highest KL grade (2, 3 or 4), Time, Treatment Group, Time x Treatment Group (Study site as a random effect)	Multiple Imputation Data	Sensitivity Analysis for Week 16 (Secondary Endpoint Analysis for other time points)
Change from Baseline to Weeks 2, 4, 8, 12, and 16 in WOMAC Pain subscale	ITT	MMRM	BL Score, BL diary average pain, Index Joint (Knee/Hip), Highest KL grade (2, 3 or 4), Time, Treatment Group, Time x Treatment Group (Study site as a random effect)	All Observed Data Including Off-Treatment	Sensitivity Analysis for Week 16 (Secondary Endpoint Analysis for other time points)
Change from Baseline to Weeks 2, 4, 8, 12, and 16 in WOMAC Pain subscale	ITT	MMRM	BL Score, BL diary average pain,	All Observed	Sensitivity Analysis for

12, and 16 in WOMAC Physical Function subscale			Index Joint (Knee/Hip), Highest KL grade (2, 3 or 4), Time, Treatment Group, Time x Treatment Group (Study site as a random effect)	Data Including Off-Treatment	Week 16 (Secondary Endpoint Analysis for other time points)
Change from Baseline to Weeks 2, 4, 8, 12, and 16 in Patient Global Assessment of Osteoarthritis	ITT	MMRM	BL Score, BL diary average pain, Index Joint (Knee/Hip), Highest KL grade (2, 3 or 4), Time, Treatment Group, Time x Treatment Group (Study site as a random effect)	All Observed Data Including Off-Treatment	Sensitivity Analysis for Week 16 (Secondary Endpoint Analysis for other time points)
Change from Baseline to Weeks 2, 4, 8, 12, and 16 in Patient Global Assessment of Osteoarthritis	ITT	CMH test	Treatment Group [1]	Mixed BOCF/LOCF	Sensitivity Analysis for PGA
Change from Baseline to Weeks 2, 4, 8, 12, and 16 in Patient Global Assessment of Osteoarthritis	ITT	CMH test	Treatment Group [1]	BOCF	Sensitivity Analysis for PGA
Change from Baseline to Weeks 2, 4, 8, 12, and 16 in Patient Global Assessment of Osteoarthritis	ITT	CMH test	Treatment Group [1]	LOCF	Sensitivity Analysis for PGA
Change from Baseline to Week 16 in WOMAC Pain subscale, shown by site (sites with n≥12)	ITT	None (summary)	NA	Multiple Imputation	Supportive summary for interaction analysis
Change from Baseline to Week 16 in WOMAC Physical Function subscale, shown by site (sites with n≥12)	ITT	None (summary)	NA	Multiple Imputation	Supportive summary for interaction analysis
Change from Baseline to Week 16 in Patient Global Assessment of Osteoarthritis, shown by site (sites with n≥12)	ITT	None (summary)	NA	Multiple Imputation	Supportive summary for interaction analysis
Change from Baseline to Week 16 in WOMAC Pain subscale, shown by country	ITT	None (summary)	NA	Multiple Imputation	Supportive summary for interaction analysis
Change from Baseline to Week 16 in WOMAC Physical Function subscale, shown by country	ITT	None (summary)	NA	Multiple Imputation	Supportive summary for interaction analysis
Change from Baseline to Week 16 in Patient Global Assessment of	ITT	None (summary)	NA	Multiple Imputation	Supportive summary for interaction analysis

Osteoarthritis, shown by country					
Missing data pattern for WOMAC Pain subscale for Baseline and Weeks 2, 4, 8, 12, and 16	ITT	None (summary)	NA	Observed Data	Supportive summary for missing data
Missing data pattern for WOMAC Physical Function subscale for Baseline and Weeks 2, 4, 8, 12, and 16	ITT	None (summary)	NA	Observed Data	Supportive summary for missing data
Missing data pattern for Patient Global Assessment of Osteoarthritis for Baseline and Weeks 2, 4, 8, 12, and 16	ITT	None (summary)	NA	Observed Data	Supportive summary for missing data
Change from Baseline to Weeks 2, 4, 8, and 12 in WOMAC Pain subscale	ITT	ANCOVA	BL Score, BL diary average pain, Index Joint (Knee/Hip), Highest KL grade (2, 3 or 4), Treatment Group (Study site as a random effect)	Multiple Imputation	Secondary Endpoint Analysis
Change from Baseline to Weeks 2, 4, 8, and 12 in WOMAC Pain subscale	ITT	ANCOVA	BL Score, BL diary average pain, Index Joint (Knee/Hip), Highest KL grade (2, 3 or 4), Treatment Group (Study site as a random effect)	BOCF	Secondary Endpoint Analysis
Change from Baseline to Weeks 2, 4, 8, and 12 in WOMAC Pain subscale	ITT	ANCOVA	BL Score, BL diary average pain, Index Joint (Knee/Hip), Highest KL grade (2, 3 or 4), Treatment Group (Study site as a random effect)	LOCF	Secondary Endpoint Analysis
Change from Baseline to Weeks 2, 4, 8, and 12 in WOMAC Physical Function subscale	ITT	ANCOVA	BL Score, BL diary average pain, Index Joint (Knee/Hip), Highest KL grade (2, 3 or 4), Treatment Group (Study site as a random effect)	Multiple Imputation	Secondary Endpoint Analysis
Change from Baseline to Weeks 2, 4, 8, and 12 in WOMAC Physical Function subscale	ITT	ANCOVA	BL Score, BL diary average pain, Index Joint (Knee/Hip), Highest KL grade (2, 3 or 4), Treatment Group (Study site as a random effect)	BOCF	Secondary Endpoint Analysis
Change from Baseline to Weeks 2, 4, 8, and 12 in WOMAC Physical Function subscale	ITT	ANCOVA	BL Score, BL diary average pain, Index Joint (Knee/Hip), Highest KL grade (2, 3 or 4), Treatment Group (Study site as a random effect)	LOCF	Secondary Endpoint Analysis

Change from Baseline to Weeks 2, 4, 8, and 12 in Patient Global Assessment of Osteoarthritis	ITT	ANCOVA	BL Score, BL diary average pain, Index Joint (Knee/Hip), Highest KL grade (2, 3 or 4), Treatment Group (Study site as a random effect)	Multiple Imputation	Secondary Endpoint Analysis
Change from Baseline to Weeks 2, 4, 8, and 12 in Patient Global Assessment of Osteoarthritis	ITT	ANCOVA	BL Score, BL diary average pain, Index Joint (Knee/Hip), Highest KL grade (2, 3 or 4), Treatment Group (Study site as a random effect)	BOCF	Secondary Endpoint Analysis
Change from Baseline to Weeks 2, 4, 8, and 12 in Patient Global Assessment of Osteoarthritis	ITT	ANCOVA	BL Score, BL diary average pain, Index Joint (Knee/Hip), Highest KL grade (2, 3 or 4), Treatment Group (Study site as a random effect)	LOCF	Secondary Endpoint Analysis
The OMERACT-OARSI response at Weeks 2, 4, 8, 12, and 16	ITT	Logistic Regression	BL Score (WOMAC Pain), BL diary average pain, Index Joint (Knee/Hip), Highest KL grade (2, 3 or 4), Treatment Group	Mixed BOCF/LOCF	Secondary Endpoint Analysis
The OMERACT-OARSI response at Weeks 2, 4, 8, 12, and 16	ITT	Logistic Regression	BL Score (WOMAC Pain), BL diary average pain, Index Joint (Knee/Hip), Highest KL grade (2, 3 or 4), Treatment Group	BOCF	Secondary Endpoint Analysis
The OMERACT-OARSI response at Weeks 2, 4, 8, 12, and 16	ITT	Logistic Regression	BL Score (WOMAC Pain), BL diary average pain, Index Joint (Knee/Hip), Highest KL grade (2, 3 or 4), Treatment Group	LOCF	Secondary Endpoint Analysis
Percentage of subjects with reduction of $\geq 30/50/70/90\%$ from Baseline to Weeks 2, 4, 8, 12, and 16 in the WOMAC Pain subscale	ITT	Logistic Regression	BL Score, BL diary average pain, Index Joint (Knee/Hip), Highest KL grade (2, 3 or 4), Treatment Group	Mixed BOCF/LOCF	Secondary Endpoint Analysis
Percentage of subjects with reduction of $\geq 30/50/70/90\%$ from Baseline to Weeks 2, 4, 8, 12, and 16 in the WOMAC Pain subscale	ITT	Logistic Regression	BL Score, BL diary average pain, Index Joint (Knee/Hip), Highest KL grade (2, 3 or 4), Treatment Group	BOCF	Secondary Endpoint Analysis
Percentage of subjects with reduction of $\geq 30/50/70/90\%$ from Baseline to Weeks 2, 4, 8, 12, and 16 in the WOMAC Pain subscale	ITT	Logistic Regression	BL Score, BL diary average pain, Index Joint (Knee/Hip), Highest KL grade (2, 3 or 4), Treatment Group	LOCF	Secondary Endpoint Analysis

Percentage of subjects with reduction of $\geq 30/50/70/90\%$ from Baseline to Weeks 2, 4, 8, 12, and 16 in the WOMAC Physical Function subscale	ITT	Logistic Regression	BL Score, BL diary average pain, Index Joint (Knee/Hip), Highest KL grade (2, 3 or 4), Treatment Group	Mixed BOCF/LOCF	Secondary Endpoint Analysis
Percentage of subjects with reduction of $\geq 30/50/70/90\%$ from Baseline to Weeks 2, 4, 8, 12, and 16 in the WOMAC Physical Function subscale	ITT	Logistic Regression	BL Score, BL diary average pain, Index Joint (Knee/Hip), Highest KL grade (2, 3 or 4), Treatment Group	BOCF	Secondary Endpoint Analysis
Percentage of subjects with reduction of $\geq 30/50/70/90\%$ from Baseline to Weeks 2, 4, 8, 12, and 16 in the WOMAC Physical Function subscale	ITT	Logistic Regression	BL Score, BL diary average pain, Index Joint (Knee/Hip), Highest KL grade (2, 3 or 4), Treatment Group	LOCF	Secondary Endpoint Analysis
Percentage of subjects with an improvement of ≥ 2 points from Baseline to Weeks 2, 4, 8, 12, and 16 in the Patient Global Assessment of Osteoarthritis	ITT	Logistic Regression	BL Score, BL diary average pain, Index Joint (Knee/Hip), Highest KL grade (2, 3 or 4), Treatment Group	Mixed BOCF/LOCF	Secondary Endpoint Analysis
Percentage of subjects with an improvement of ≥ 2 points from Baseline to Weeks 2, 4, 8, 12, and 16 in the Patient Global Assessment of Osteoarthritis	ITT	Logistic Regression	BL Score, BL diary average pain, Index Joint (Knee/Hip), Highest KL grade (2, 3 or 4), Treatment Group	BOCF	Secondary Endpoint Analysis
Percentage of subjects with an improvement of ≥ 2 points from Baseline to Weeks 2, 4, 8, 12, and 16 in the Patient Global Assessment of Osteoarthritis	ITT	Logistic Regression	BL Score, BL diary average pain, Index Joint (Knee/Hip), Highest KL grade (2, 3 or 4), Treatment Group	LOCF	Secondary Endpoint Analysis
Percentage of subjects with reduction of $\geq 30/50\%$ from Baseline to Week 16 in the WOMAC Pain subscale, separately for Week 8 Responders and Non-Responders (same definition as Week 16)	ITT	Logistic Regression	BL Score, BL diary average pain, Index Joint (Knee/Hip), Highest KL grade (2, 3 or 4), Treatment Group	Mixed BOCF/LOCF	Exploratory Analysis
Reduction of $>0\%$, $\geq 10\%$, to $\geq 90\%$ (in steps of 10%) and $=100\%$ from Baseline to Week 16 in the WOMAC Pain subscale	ITT	None (summary and plot)	NA	Mixed BOCF/LOCF	Summary of secondary endpoint
Reduction of $>0\%$, $\geq 10\%$, to $\geq 90\%$ (in steps of 10%) and $=100\%$ from Baseline to Week 16 in the WOMAC Pain subscale	ITT	None (summary)	NA	BOCF	Summary of secondary endpoint

Reduction of >0%, ≥10%, to ≥90% (in steps of 10%) and =100% from Baseline to Week 16 in the WOMAC Pain subscale	ITT	None (summary)	NA	LOCF	Summary of secondary endpoint
Reduction of >0%, ≥10%, to ≥90% (in steps of 10%) and =100% from Baseline to Week 16 in the WOMAC Physical Function subscale	ITT	None (summary and plot)	NA	Mixed BOCF/LOCF	Summary of secondary endpoint
Reduction of >0%, ≥10%, to ≥90% (in steps of 10%) and =100% from Baseline to Week 16 in the WOMAC Physical Function subscale	ITT	None (summary)	NA	BOCF	Summary of secondary endpoint
Reduction of >0%, ≥10%, to ≥90% (in steps of 10%) and =100% from Baseline to Week 16 in the WOMAC Physical Function subscale	ITT	None (summary)	NA	LOCF	Summary of secondary endpoint
Change from Baseline to Weeks 2, 4, 8, 12, and 16 in the WOMAC Stiffness subscale	ITT	ANCOVA	BL Score, BL diary average pain, Index Joint (Knee/Hip), Highest KL grade (2, 3 or 4), Treatment Group (Study site as a random effect)	Multiple Imputation	Secondary Endpoint Analysis
Change from Baseline to Weeks 2, 4, 8, 12, and 16 in the WOMAC Average Score	ITT	ANCOVA	BL Score, BL diary average pain, Index Joint (Knee/Hip), Highest KL grade (2, 3 or 4), Treatment Group (Study site as a random effect)	Multiple Imputation	Secondary Endpoint Analysis
Change from Baseline to Weeks 2, 4, 8, 12, and 16 in the WOMAC Item: Pain When Walking on a Flat Surface	ITT	ANCOVA	BL Score, BL diary average pain, Index Joint (Knee/Hip), Highest KL grade (2, 3 or 4), Treatment Group (Study site as a random effect)	Multiple Imputation	Secondary Endpoint Analysis
Change from Baseline to Weeks 2, 4, 8, 12, and 16 in the WOMAC Item: Pain When Going Up or Down Stairs	ITT	ANCOVA	BL Score, BL diary average pain, Index Joint (Knee/Hip), Highest KL grade (2, 3 or 4), Treatment Group (Study site as a random effect)	Multiple Imputation	Secondary Endpoint Analysis
Change from Baseline to Days 1, 2, 3, 4, 5, 6, 7, and to Weeks 1, 2, 3, 4, 6, 8, 10, 12, and 16 in the weekly average pain score in the index joint	ITT	ANCOVA	BL Score, Index Joint (Knee/Hip), Highest KL grade (2, 3 or 4), Treatment Group (Study site as a random effect)	Multiple Imputation	Secondary Endpoint Analysis

Time to treatment discontinuation due to lack of efficacy (up to Week 16)	ITT	Log-Rank (with KM estimates)	Treatment Group	Observed	Secondary Endpoint Analysis
Incidence of treatment discontinuation due to lack of efficacy (up to Week 16)	ITT	Logistic Regression	BL WOMAC Pain, BL diary average pain, Index Joint (Knee/Hip), Highest KL grade (2, 3 or 4), Treatment Group	Observed	Secondary Endpoint Analysis
Incidence of rescue medication use during Weeks 2, 4, 8, 12, and 16	ITT	Logistic Regression	BL WOMAC Pain, BL diary average pain, Index Joint (Knee/Hip), Highest KL grade (2, 3 or 4), Treatment Group	LOCF	Secondary Endpoint Analysis
Number of days of rescue medication use during Weeks 2, 4, 8, 12, and 16	ITT	Negative Binomial Model	BL WOMAC Pain, BL diary average pain, Index Joint (Knee/Hip), Highest KL grade (2, 3 or 4), Treatment Group	LOCF	Secondary Endpoint Analysis
Amount (mg) of rescue medication taken during Weeks 2, 4, 8, 12, and 16	ITT	Negative Binomial Model	BL WOMAC Pain, BL diary average pain, Index Joint (Knee/Hip), Highest KL grade (2, 3 or 4), Treatment Group	LOCF	Secondary Endpoint Analysis
EQ-5D-5L dimensions (Mobility; Self-care; Usual activities; Pain/Discomfort; Anxiety/Depression), EQ-VAS and Overall Health Utility at Baseline and Weeks 8 and 16	ITT	Summary	NA	Observed	Secondary Endpoint Analysis
WPAI endpoints (% work time missed; % impairment while working; % overall work impairment; % activity impairment) at Week 16	ITT	ANCOVA	BL score, BL diary average pain, Index Joint (Knee/Hip), Highest KL grade (2, 3 or 4), Treatment Group (study site as a random effect)	Observed	Secondary Endpoint Analysis
Healthcare Resource Utilization at Baseline, Weeks 24 and 40	ITT	Descriptive Summary	Treatment group	Observed	Secondary Endpoint Analysis
Change from baseline to Weeks 2, 4, 8, 12, 16, 24, and 40 in the NIS score, and Change from Baseline to Worst post-Baseline NIS score	ITT	CMH test	Treatment Group [1]	LOCF (Weeks 2, 4, 8, 12, 16, 24, & 40), Worst post-baseline score	Safety Endpoint Analysis
Survey of Autonomic Symptoms (SAS), number of symptoms and total impact score (by visit and change from Baseline)	ITT	Summary	NA	Observed	Safety Endpoint Analysis

[1] CMH test will be stratified by the levels of the combined stratification parameters (6 levels). If there are <15 subjects in any combined stratification level then the CMH test will be unstratified

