3.5. Safety Endpoints

- *Adverse Events;*
- *Standard safety assessments (safety laboratory testing [chemistry, hematology], sitting vital signs, electrocardiogram (ECG [12-lead]));*
- *Joint safety adjudication outcomes;*
- *Total joint replacements;*
- *Neurologic examination (Neuropathy Impairment Score [NIS]);*
- *Orthostatic (supine/standing) blood pressure assessments;*
- *Survey of Autonomic Symptom scores;*
- *Anti-drug antibody (ADA) assessments;*
- *Physical examinations.*

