4. ANALYSIS SETS

Data for all subjects will be assessed to determine if subjects meet the criteria for inclusion in each analysis population prior to unblinding and releasing the database and classifications will be documented per standard operating procedures.

If a subject was:

- Randomized but not treated, then that subject will be excluded from all efficacy and safety analyses.
- Treated but not randomized, then by definition that subject will be excluded from the efficacy analyses, but will be reported under the treatment they actually received for all safety analyses.
- Randomized but received incorrect treatment, then that subject will be reported under their randomized treatment group for all efficacy analyses, but will be evaluated on a case-by-case basis for presentation for safety analyses. Decisions will be made before unblinding.

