4.1. Full Analysis Set

The intent to treat (ITT) analysis set is the primary analysis set for efficacy analyses. It consists of all randomized subjects who received at least one dose of SC study medication (either tanezumab or placebo SC). This analysis set is used in the presentations of all

efficacy data, and all data listings, and is labeled as the ‘ITT Analysis Set’ or ‘ITT Population’.

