4.3. Safety Analysis Set

The safety analysis set is defined as all subjects treated with tanezumab or placebo SC (see beginning of Section 4 for further details). This analysis set will be labeled as the ‘Safety Analysis Set’ or ‘Safety Population’ in the corresponding data analyses and summary presentations.

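### SAP Appendix 1 assigns the NIS and SAS safety analyses to the ITT set, which conflicts with Section 4 for any treated but non-randomised subject and leaves the grouping of incorrectly treated subjects unclear

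*SAP*

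**What the plan says.** SAP Section 3.5 lists both measures among the safety endpoints: "Neurologic examination (Neuropathy Impairment Score [NIS"]) and "Survey of Autonomic Symptom scores". Their reporting is described in Sections 6.6 and 6.6.3, under safety. Neither section names an analysis set for them.

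The analysis set appears only in Appendix 1. The NIS row (change to each visit and "Change from Baseline to Worst post-Baseline NIS score", by CMH test) and the SAS row ("Survey of Autonomic Symptoms (SAS), number of symptoms and total impact score (by visit and change from Baseline"), summary only) both have ITT in the analysis-set column and a safety label in the objective column.

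On the sets themselves:

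- Section 4.1 ties ITT to efficacy and makes randomisation a condition of membership: "It consists of all randomized subjects who received at least one dose of SC study medication".
- Section 4.3: "The safety analysis set is defined as all subjects treated with tanezumab or placebo SC". Randomisation is not a condition.
- Section 4: a subject treated but not randomised is left out of efficacy, but "will be reported under the treatment they actually received for all safety analyses".
- Section 4: a randomised subject given the wrong treatment stays in the randomised group for efficacy. For safety, the presentation is decided case by case before unblinding.

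Section 5.2 makes ITT the default for efficacy analyses only. The SAP does not present the NIS and SAS entries as a deliberate exception.

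**The concern.** Two analyses that the SAP itself classes as safety are assigned to the set it reserves for efficacy. Appendix 1 is the only place that names a set for them, so a programmer working from it would use ITT.

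Two things follow. First, a person exposed to study drug without having been randomised would be missing from the NIS and SAS tables, although Section 4 wants that person in every safety analysis. Other safety tables, built on the Safety Analysis Set, would include them. Second, for a subject who received the wrong treatment, the ITT label makes it unclear which of the two Section 4 grouping rules applies.

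The SAP gives neurological findings several dedicated outputs: NIS by visit and by worst change, consultation outcomes, and persistence of findings. They should describe the same exposed population as the rest of the safety report, or the SAP should say why they do not.

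**Working it through.** No calculation in the SAP is at issue. The check compares set membership and grouping under the two instructions.

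Let R be the randomised subjects and T the subjects who received at least one SC dose of study medication.

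- ITT (Section 4.1) = R and T.
- Safety (Section 4.3) = T.
- Safety minus ITT = T and not R, that is, subjects treated but not randomised.

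Four kinds of subject cover every case:

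| Subject | Section 4 rule for safety | Appendix 1 with ITT | Conflict? |
|---|---|---|---|
| Randomised, not treated | Excluded | Excluded (not dosed) | No |
| Randomised, correct treatment | Included in own arm | Included in own arm | No |
| Treated, not randomised | Included, by treatment received | Excluded by definition | Yes, direct |
| Randomised, wrong treatment | Included, arm decided case by case | Included, arm not stated | Unclear |

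The difference in denominator between the two sets is therefore exactly the number of treated but non-randomised subjects. The difference in grouping is limited to the incorrectly treated subjects. The SAP gives neither count. If both are zero, the NIS and SAS results are the same under either label.

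A further check is whether the Safety set can be used in both rows as the methods stand.

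- SAS: yes. The row is a descriptive summary of observed data with no model terms.
- NIS: not completely. Section 5.2.3 and the Appendix 1 footnote stratify the CMH test by index joint (2 levels) and highest Kellgren-Lawrence grade (3 levels), giving 2 × 3 = 6 strata. Section 3.4.1 says analysis models take the strata as entered at randomisation, and keeps the case report form strata for descriptive summaries and subgroups. If that rule also covers the CMH test, which is the natural reading, a subject who was never randomised has no stratum. Such a subject could enter only the unstratified fallback, which applies when any of the 6 combinations has fewer than 15 subjects, or would need an added rule.

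So changing the label resolves the SAS row fully, while the NIS row also needs a line on strata.

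**The case against.** The best defence is that almost nothing turns on this. ITT here already requires a dose, so both sets contain only treated subjects, and the SAP does not say that any subject was, or is expected to be, treated without randomisation. The body of the SAP places both measures under safety, so Section 4 could be said to govern them whatever the appendix says. Appendix 1 is a table of efficacy analyses in which the other rows use ITT or the per-protocol set, so the entry looks like a column value carried down. All of this is fair, and it bears on size. It does not remove the conflict: Section 4 writes rules for exactly these subjects, and the appendix entry contradicts one of them.

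It could also be argued that the NIS test needs randomisation strata and hence randomised subjects. That has some force for NIS, but it cannot explain the SAS row, which has no stratification.

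A reader might go further in two ways that the SAP does not support.

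- One might infer that incorrectly treated subjects would be counted under an arm whose treatment they did not receive, for instance as placebo. Appendix 1 says only ITT. The randomised-group rule in Section 4 is confined to efficacy, and the same bullet gives safety a case-by-case rule. The label makes the grouping ambiguous; it does not order that outcome.
- One might put a size on the effect by noting that one subject in an arm of about 230 is 1/230 = 0.43 percentage points. That is arithmetic on a hypothetical subject. The NIS test compares mean scores over change categories and the SAS is summarised as symptom counts and impact scores, so neither is an analysis of a rare-event incidence.

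Nor would the Safety set make all denominators agree. NIS uses LOCF without carrying baseline forward and SAS uses observed data, so both can differ from the adverse event tables under either set.

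**Conclusion.** The point stands as a minor internal contradiction. For a treated but non-randomised subject, Section 4 and Appendix 1 give opposite instructions on the NIS and SAS analyses. For an incorrectly treated subject, they leave the grouping rule unclear.

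The size is small. It is nil if no such subjects exist, and it cannot be put into figures from the SAP, which reports no counts. The conclusion rests on the SAP's own definitions of the two sets, on its own labelling of the rows as safety analyses, and on the absence of any stated exception. It does not touch the co-primary or other efficacy analyses, for which ITT is the stated set.

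**What to change.** 1. In Appendix 1, change the analysis set from ITT to Safety in the NIS and SAS rows. Section 4's safety handling then governs both who is included and how incorrectly treated subjects are grouped.
2. In Section 5.2.3 or 6.6.3, add a sentence for the stratified NIS CMH test: a subject without randomisation strata is assigned the strata from the case report form, or else appears in the descriptive summary only. Choose one before unblinding.
3. It would help to name the Safety Analysis Set in Sections 6.6 and 6.6.3, which now name none for these measures.

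If ITT was intended, say so in Section 4 as an exception to the rule for all safety analyses, and give the reason.

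The cost is two table cells and one or two sentences. No new data or additional analysis is needed. Section 4 already requires set membership to be settled before unblinding, so the correction belongs at that step.
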